13.2. Missing Date Imputation for Missing or Partial Dates

Table 3: Algorithm for Treatment Emergence of Adverse Events.			
AE start date	AE end date	RULE for TEAE definition	RULE for definition of study period for TEAEs only: “On Treatment” / “On follow-up”
Known	Known, Partial or Missing	If start date < IMP start date, then not TEAE If start date ≥ IMP start date, then TEAE	If start date > date of last IMP administration, then “On Follow-up”. Otherwise, “On Treatment”
Partial, but known components show that it cannot be on or after IMP start date	Known, Partial or Missing	Not TEAE	Not applicable
Partial, could be on or after IMP start date OR Missing	Known	If stop date < IMP start date, then not TEAE If stop date ≥ IMP start date, then TEAE	If TEAE, then “On Treatment”
	Partial	Impute stop date as latest possible date (i.e. last day of month if only day is missing, Dec if only month is missing, 31 st Dec if day and month are both missing, then: If stop date < IMP start date, then not TEAE If stop date ≥ IMP start date, then TEAE	
	Missing	Assumed TEAE	

Table 4: Algorithm for Prior / Concomitant medications.		
MEDICATION start date	MEDICATION end date	RULE for Prior / Concomitant definition
Known	Known	If stop date < IMP start date, then “prior” If stop date ≥ IMP start date, then “concomitant”
	Partial	Impute stop date as latest possible date (i.e. last day of month if only day is missing, Dec if only month is missing, 31 st Dec if day and month are both missing, then: If stop date < IMP start date, then “prior” If stop date ≥ IMP start date, then “concomitant”
	Missing	Assign as concomitant
Partial OR Missing	Known	If stop date < IMP start date, then “prior” If stop date ≥ IMP start date, then “concomitant”
	Partial	Impute stop date as latest possible date (i.e. last day of month if only day is missing, Dec if only month is missing, 31 st Dec if day and month are both missing, then: If stop date < IMP start date, then “prior” If stop date ≥ IMP start date, then “concomitant”
	Missing	Assign as concomitant

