9.3 RECORDING ADVERSE EVENTS

AE data should be obtained through observation of the patient, from any information volunteered by the patient, and through patient questioning.

Adverse Events:

All AEs (non-serious and serious) that occur during the course of the study will be recorded in the eCRF. Any pre-existing medical conditions or signs/symptoms present in a patient prior to the start of the study (i.e., before informed consent is signed) should be specified in the dedicated eCRF sections. Subsequent to signing an informed consent form, all untoward medical occurrences that occur during the course of the study must be documented on eCRF. AEs will be collected till the last follow-up visit (week 8).

When possible, signs and symptoms indicating a common underlying pathology should be documented as one comprehensive event. For each recorded event, the AE documentation must include the onset date, outcome, resolution date (if event is resolved), intensity (i.e., severity), any action with study treatment taken as a result of the event, and an assessment of the adverse event relationship to the study treatment.

Serious Adverse Events:

The Investigator must record all SAEs, including sight-threatening events, occurring at any time during the study (after signature of the informed consent) regardless of presumed causal relationship, on the Serious Adverse Event form in the eCRF of the EDC system within 24 hours of learning of the event; information on the SAE must also be recorded on a specific Non-Carbon Repeat SAE form (included in the Investigator's Site File).

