9.3.3 Severity of AEs

The Investigator will grade the severity of any AE using the definitions in the Table below. For each episode, the highest severity grade attained should be reported.

Table 8: Severity of the Adverse Event

Severity	Description
Mild	Grade 1 - Does not interfere with patient's usual function (awareness of symptoms or signs, but easily tolerated [acceptable]).
Moderate	Grade 2 - Interferes to some extent with patient's usual function (enough discomfort to interfere with usual activity [disturbing]).
Severe	Grade 3 - Interferes significantly with patient's usual function (incapacity to work or to do usual activities [unacceptable])

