10.6.5 Analysis of Safety Variables

Adverse events (AEs) will be coded by System Organ Class (SOC) and Preferred Term (PT), using the Medical Dictionary for Regulatory Activities (MedDRA).

Treatment-emergent AEs (TEAEs) are all events occurring or worsening after the first dose of the IMP. TEAEs will be presented by treatment arm in terms of number of AEs and their incidence by System Organ Class (SOC) and Preferred Terms (PT) using MedDRA. Analyses will be provided also by seriousness, relationship to treatment, severity, and study period

(treatment or follow-up).

Individual AEs will be listed in patient data listings.

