4.5.3. Adverse Event Data

Algorithm to impute partial or missing end dates is described in [Appendix 13.2](#), but partially or missing AE start dates will not be imputed. The rule for the classification of AEs and TEAEs is also shown in [Appendix 13.2](#) with details on the derivation of the period for TEAEs after date imputation.

In case one or more AE characteristics are missing (for example severity and relationship to study drug), the most conservative approach will be taken (in the example, the AE will be considered severe, and drug related).

In listings of AE data, the partial dates as collected will be displayed. Imputed dates with details of what has been imputed in brackets (e.g. D if day is imputed, M if month, DM if both) will be provided.

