9.1. Adverse Events

An Adverse Event (AE) is defined as any untoward medical occurrence in a patient or clinical investigation patient administered a medicinal product and which does not necessarily have a causal relationship with this treatment. An AE can therefore be any unfavorable and unintended sign (including an abnormal laboratory finding), symptom, or disease temporally associated with the use of a medicinal product, whether or not related to the medicinal product.

Treatment-emergent AEs (TEAEs) are defined as AEs that are reported or worsened on or after the first dose of IMP.

Adverse events will be coded according to latest version of MedDRA. Unless otherwise specified, AEs will be summarized by treatment arm and by SOC and PT, with SOC sorted in descending order of patient incidence and PTs within each SOC in descending order of patient incidence in Total group, for each treatment period (“On Treatment period”, “On Follow-up period” and “Overall”). If the total frequency for any 2 or more PTs is equal, the PTs will be presented in alphabetical order.

When summarizing the number and percentage of patients with an event, patients with multiple occurrences of the same AE or a continuing AE will be counted only once. Patients will be presented according to the highest severity (the strongest relationship) in the summaries by severity (of related AEs), if patients reported multiple events under the same SOC and/or PT.

Ocular TEAEs will be summarized separately from non-ocular TEAEs. Ocular TEAEs will be summarized for the Study Eye and the fellow eye. Non-ocular TEAEs will be summarized regardless of the Study Eye or the fellow eye.

By-patient listings of ocular and non-ocular AEs will be presented by treatment and ordered by site.

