9.1.7. Adverse Events Leading to Treatment Discontinuation

TEAEs with a study treatment action taken of ‘Drug Withdrawn’ will be considered as TEAEs leading to treatment discontinuation and will be summarized by SOC and PT.

A by-patient listing will also be provided for all adverse events leading to treatment discontinuation and ordered by site.

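### SAP Table 3 has no worsening branch, so a run-in adverse event that worsens on study drug under the same record is classed as not treatment-emergent, against SAP 9.1 and Protocol 10.6.5

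*SAP*

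**What the plan says.** The two definitions agree that worsening counts. SAP 9.1: "Treatment-emergent AEs (TEAEs) are defined as AEs that are reported or worsened on or after the first dose of IMP". Protocol 10.6.5: "Treatment-emergent AEs (TEAEs) are all events occurring or worsening after the first dose of the IMP".

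SAP 4.5.3 points to Appendix 13.2 for more than date imputation: "The rule for the classification of AEs and TEAEs is also shown in" that appendix. Table 3 there sorts events by how much of the start date is known. If it is known, then for any end date, "If start date < IMP start date, then not TEAE". If it is partial but must fall before IMP start, the event is again not a TEAE. Only the row headed "Partial, could be on or after IMP start date OR Missing" looks at the end date. No row refers to severity or worsening.

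On data collection, Protocol 9.3 requires recording from consent onwards: "Subsequent to signing an informed consent form, all untoward medical occurrences that occur during the course of the study must be documented on eCRF". The fields it lists are onset date, outcome, resolution date, intensity, action taken with study treatment, and relationship. Protocol 9.3.3 adds: "For each episode, the highest severity grade attained should be reported".

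**The concern.** A programmer who builds the TEAE flag from Table 3 will not produce the population that SAP 9.1 defines. The SAP's precedence over the protocol (SAP Section 1) does not settle this, because the SAP disagrees with itself.

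The design makes the gap relevant. Every patient uses the new vehicle for 12 ± 2 days before randomisation, and adverse events are recorded throughout, so some may be ongoing on Day 1. The new formulation was prepared because of poor tolerability: Protocol 6.2 cites eye pain in 42% to 63.5% of patients in earlier dry eye studies. Aggravation on active drug of an ocular event already present is one plausible form of that problem, and the definition's worsening clause is there to catch it.

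Several summaries depend on the flag: the overall summary (SAP 9.1.1), related events and ADRs (9.1.2, 9.1.10), severity (9.1.4), serious events (9.1.5), and events leading to treatment or study discontinuation (9.1.7, 9.1.8). For example, under 9.1.7, "TEAEs with a study treatment action taken of ‘Drug Withdrawn’ will be considered as TEAEs leading to treatment discontinuation", so an event that Table 3 has already excluded cannot enter that table.

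**Working it through.** This is a check of a rule. The plan gives no figure to reproduce.

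**Inputs**
- IMP start is Day 1. SAP 7.3.1 takes the first treatment date from the Randomization form, and Protocol 6.5 places the first IMP administration at the baseline visit. The run-in lies before it.
- Rule A, Table 3. Known start: TEAE if start ≥ Day 1. Partial start certainly before Day 1: not TEAE. Start missing, or partial and possibly on or after Day 1: TEAE if the stop date is ≥ Day 1 or missing.
- Rule B, SAP 9.1 and Protocol 10.6.5. TEAE if onset or worsening is on or after Day 1.

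**Comparison on seven constructed events**

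| Event | Table 3 | Definition |
|---|---|---|
| Known start Day −6, worsens Day 3, stops Day 10 | not TEAE | TEAE |
| Known start Day −6, worsens Day 3, ongoing | not TEAE | TEAE |
| Partial start certainly before Day 1, worsens Day 3, stops Day 10 | not TEAE | TEAE |
| Partial start possibly on or after Day 1, worsens Day 3, stops Day 10 | TEAE | TEAE |
| Missing start, worsens Day 3, ongoing | TEAE | TEAE |
| Known start Day −6, no worsening, stops Day 2 | not TEAE | not TEAE |
| Known start Day 3 | TEAE | TEAE |

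The rules disagree on the first three events, all with onset known to be before Day 1 and worsening after it. With a worsening test added to Table 3, all seven agree. Three of seven describes the test set and is not an expected rate.

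**Does data collection close the gap?** It would if every worsening were entered as a new record with its own onset date. Neither document requires that. Protocol 9.3.3 keeps the highest grade per episode, and the fields listed in Protocol 9.3 include no date of worsening.

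**Size (assumed rates).** Let a and v be the proportions of an active arm and the vehicle arm with such an event and no other TEAE.
- Patients lost per 97-patient arm: 97 × 0.01 = 0.97, about 1, up to 97 × 0.10 = 9.7, about 10.
- The active-minus-vehicle difference in TEAE incidence is understated by a − v. If a = v it is unchanged. If a = 10% and v = 1%, the loss is 10 − 1 = 9 percentage points, the extreme of the assumed range.

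**The case against.** The text conflict is hard to dispute. The case on the other side is that its consequences are easily overstated, and most of that case stands.

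- **A reader might infer that such an event survives only in listings.** It need not. SAP 5.1 tabulates reasons for treatment discontinuation by arm, including adverse event and tolerability. SAP 9.3 counts tolerability discontinuations from the End of Treatment page, without using the TEAE flag. SAP 9.1.6 summarises AESIs with no stated TEAE restriction.
- **A reader might infer that the tolerability signal is erased.** It is not. SAP 8.2.2.1 compares change from baseline in an ocular pain score at Weeks 4 and 8, and baseline follows the run-in, so pain still aggravated at those visits would register. Aggravation that settles before Week 4 might not.
- **A reader might infer that worsening must stay on the original record.** The documents do not say so. Protocol 9.3.3 does not define an episode. Protocol 9.2 asks for an AE report when a concomitant condition changes for the worse, so a condition present before consent that worsens on IMP should yield a record with a post-IMP start date. The eCRF completion guidelines mentioned in Protocol 11.9 are not available and may contain a split-record rule. Still, nothing in the protocol or SAP forces a new record for an AE already open.
- **Table 3 does not always rest on the start date.** With a missing or ambiguous start date the end date decides, and the event can be a TEAE.

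One further defence fails. The safety endpoint in Protocol 3.1 speaks of TEAEs through the run-in, which might suggest that run-in vehicle counts as IMP. SAP 7.3.1 rules that out, and Table 3 provides only on-treatment and follow-up periods.

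**Conclusion.** The point holds as an internal contradiction in the SAP that should be corrected before database lock. Table 3, as written, cannot deliver the definition in SAP 9.1 and Protocol 10.6.5 for an event that starts in the run-in, is ongoing on Day 1 and worsens on IMP under the same record. That conclusion rests on the text alone.

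The size is unknown. The documents give no run-in AE rate, no worsening rate and no record-splitting rule, so the 1 to 10 patients per arm is illustrative. Table 3 applies equally to all arms. A reader might infer a built-in bias in favour of rhNGF, but the documents do not support that: incidence is pulled towards no difference only if active drug aggravates such events more often than vehicle. That is plausible given the earlier eye-pain figures, but it is not established for these concentrations. No efficacy analysis is affected.

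**What to change.** 1. **Table 3.** Add a branch: an AE that starts before IMP start, is ongoing at IMP start, and increases in severity or becomes serious on or after IMP start is a TEAE. Assign its study period by the date of worsening, using Table 3's existing cut at the last IMP administration.
2. **eCRF completion instruction.** When an AE ongoing at first IMP dose increases in grade, sites record the date of worsening or open a new record.
3. **Records without a worsening date.** Decide TEAE status in the masked data review, before unmasking. The default should be conservative, in line with how SAP 4.5.3 treats missing severity or relationship: where worsening on IMP cannot be excluded, class the event as a TEAE.

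An automatic rule that any ongoing AE with drug withdrawn is a TEAE would go beyond the definition, because a drug can be withdrawn for an event that never worsened. Rules built on the grade at Visit 2 or on a separate seriousness date would need data that the documents do not describe as collected.

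The cost is a short SAP revision, one derivation in the AE dataset, a completion note and some review time. TEAE counts may rise slightly. If data collection has already closed, item 2 falls away and item 3 carries more of the load.

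### SAP Table 3 counts an adverse event with a partial start date as On Treatment even when its known month and year fall wholly after the last dose

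*SAP*

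**What the plan says.** SAP 9.1 summarises AEs by arm, SOC and PT for the On Treatment period, the On Follow-up period and Overall. Protocol 10.6.5 also calls for TEAE analyses by study period. The period comes from the last column of Table 3 in SAP 13.2, which has three kinds of row:

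- **Known start date**, whatever the state of the end date: "If start date > date of last IMP administration, then “On Follow-up”. Otherwise, “On Treatment".
- **Incomplete start date that must precede the first dose**, described as "Partial, but known components show that it cannot be on or after IMP start date": the event is not treatment-emergent, so no period applies.
- **"Partial, could be on or after IMP start date OR Missing"**: treatment emergence is decided from the end date, and the period is then "If TEAE, then “On Treatment".

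SAP 4.5.3 refers the period derivation to this appendix and adds that "partially or missing AE start dates will not be imputed".

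**The concern.** Table 3 uses what is known of a partial start date at one boundary only. If the month and year show that the event began before the first dose, the event is excluded. If they show that it began after the last dose, nothing happens: the event stays in the row for ambiguous dates and is labelled On Treatment. As no start date is imputed, no other rule moves it.

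At stake is the by-period display of new onsets. A reader will use it to see whether events such as eye pain, common enough in earlier rhNGF studies to motivate the new formulation (Protocol 6.2), begin only while dosing continues or also afterwards. Any such error adds to the On Treatment count and takes from the On Follow-up count, never the reverse.

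**Working it through.** The plan states no figure on this point, so there is none to reproduce. The check applies the rule as written to a test case and then sets out how often a month alone would settle the period.

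**Test case.** First dose 3 June (Day 1), last dose 30 June (Day 28).

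| AE start as recorded | End date | Table 3 row | Period assigned |
|---|---|---|---|
| 10 July | known or missing | known start | On Follow-up |
| July, day missing | known (12 July) | partial start | On Treatment |
| July, day missing | missing | partial start | On Treatment |

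All of July lies after 30 June, so the last two rows are wrong on the information recorded. The first row shows that only the start date has to be complete; a missing end date does not keep an event out of follow-up.

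**How often the month alone is decisive.** Inputs from the SAP schedule (13.1): end of treatment Day 28, end of follow-up Day 56, so 28 follow-up days (Days 29 to 56). Assumptions, not from the documents: last dose exactly on Day 28, first-dose dates uniform over a 366-day year, onset uniform over follow-up, month and year known and only the day missing.

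1. Total follow-up days: 366 × 28 = 10,248.
2. If the last dose falls r days before the end of its month, the follow-up days in a later month number 28 − r for r = 0 to 27, and none for larger r.
3. Every month has at least 28 days, so each contributes 28 + 27 + … + 1 = 28 × 29 / 2 = 406.
4. Over twelve months: 12 × 406 = 4,872.
5. Share: 4,872 / 10,248 = 47.5%.

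A direct enumeration of all 366 first-dose dates gives the same 4,872 of 10,248. Under Table 3 as written, a day-missing start is assigned to follow-up in 0 of the 10,248 cases. With the added row it would be assigned correctly in 4,872. The other 5,376 share a month with the last dose, are truly ambiguous, and would stay On Treatment.

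**The case against.** The strongest reply is that assigning incompletely dated events to treatment is a deliberate conservative convention, in line with SAP 4.5.3, which takes the cautious value when severity or relationship is missing. The rule is the same in every arm, safety is not formally tested (SAP 9), and the listings show partial dates as collected, so affected events can be found. All of this stands for ambiguous dates. It does not cover dates that are not ambiguous: caution is a reason for resolving doubt towards the drug, and here there is none.

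A reader might go further in four ways that the documents do not support:

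- *That the split shows whether events resolve after dosing stops.* It does not. The period is set by onset, so an event running from Day 5 to Day 50 is On Treatment under either rule. Resolution is recorded separately (Protocol 9.3).
- *That partial dates are commoner in follow-up because visits are sparser.* Visit spacing alone does not show this. A follow-up diary is dispensed at Visit 4 and retrieved at Visit 5 (Protocol 8.2), AE records must carry an onset date (Protocol 9.3), and edit checks can raise queries (Protocol 12.1).
- *That patients who stop early are the most affected.* Nothing in the documents shows this, and events that led them to stop began before the last dose, so On Treatment is right for those.
- *That about half of follow-up events are misplaced.* The 47.5% applies only to events that begin in follow-up and have a partial start date with month and year known.

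One point of reading also remains. In the extracted table the On Treatment entry is printed beside the known-end-date sub-row, and the two cells below are blank. A merged cell is the likely layout. If it is not merged, those sub-rows have no period rule and still cannot reach follow-up.

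**Conclusion.** The point holds as a minor defect in a classification rule. Table 3 puts a treatment-emergent event with a partial start date On Treatment without checking its known month and year against the last dose, so some events that certainly began after dosing are tabulated in the wrong period. The by-period onset counts can be biased one way only. TEAE status, Overall counts and every endpoint are unchanged.

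The effect on the tables cannot be sized from the documents, because they do not say how many AE start dates are partial. The number is probably small and the effect could be nil. The 47.5% illustrates how often a month alone would settle the matter under the assumptions stated; it is not an estimate of the error rate. The conclusion assumes that the On Treatment cell spans all three end-date sub-rows.

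**What to change.** Add one row to Table 3: *Partial start date whose known components show it is after the date of last IMP administration: if TEAE, then On Follow-up.* Apply it before the existing partial-or-missing row, which then covers only ambiguous partial dates and fully missing dates and keeps On Treatment for both. State that this On Treatment cell covers all three end-date sub-rows.

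The cost is one table row and one programming condition, made before unmasking. No endpoint, alpha level or Overall count changes, and the conservative handling of doubtful dates is kept.

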13.3. SAS Code for Primary Analysis

Step 1: Multiple Imputation

```
PROC SORT data=efficacy;  
  by USUBJID;  
RUN;
```

```
PROC MI data=efficacy nimpute=50 out=mi_data min=0 max=100 seed= 47292748; *score range: 0-100;  
  class TRTPN;  
  var V2 V4 V5; *V2=baseline, V4=Week 4, V5=Week 8;  
  FCS regression;  
  mnar model(V2 V4 V5/ modelobs=(TRTPN='3')); *Vehicle group has TRTPN=3;  
RUN;
```

Data will be transformed to short format by AVISITN before applying multiple imputation.
The MI method will be used for both primary and secondary analyses after applying appropriate ICE handling strategies.

Step 2: MMRM Model

```
PROC MIXED data= mi_data_long;  
  by _imputation;  
  class TRTPN AVISITN USUBJID;  
  model CHG=BASE TRTPN AVISITN TRTPN*AVISITN / DDFM=KR CL;  
  repeated AVISITN/subject=USUBJID type=UN;  
  lsmeans TRTPN*AVISITN/diff cl;  
  ods output lsmeans=lsM diffs=diffM;  
RUN;
```

Data will be transformed back to long format by combining visits before applying MMRM model.
If model fails to converge, the “type=UN” will be replaced by “type=CS”.
This model is the essential model for primary endpoint. Appropriate adjustments may be made based on modified Estimand strategies and sensitivity analyses.

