10 STATISTICS

10.1 SAMPLE SIZE

The sample size of the study is calculated based on results from the previous study NGF0118 using the subgroup of patients with baseline SANDE Global Score > 50. Expecting a mean difference of about 11 points (with unequal standard deviations in the active and vehicle groups: observed mean changes (SD) were -28.2 (26.36) and -17.4 (20.29) for IMP and vehicle, respectively) in improvement of SANDE Global Score from baseline to Week 8 in favor of rhNGF ophthalmic (eye drop) formulation, a total sample size of 276 evaluable patients (92 per group) is needed. This will allow to achieve an overall power of 80% for demonstrating superiority of at least one concentration of rhNGF ophthalmic formulation over vehicle in the improvement of SANDE Global Score from baseline to week 8, with an overall one-sided alpha of 0.025.

The sample size calculation takes into consideration a Bonferroni correction for two comparisons (2 concentration groups versus vehicle), i.e., the alpha level has been set to 0.0125 one-sided for each comparison.

Assuming a 5% rate of patients not evaluable for primary analysis after enrollment, the total number of patients to be enrolled in the study will be about 291 (97 per group). Enrollment will be competitive.

In Dompé previous studies, a screen failure rate of about 20% has been observed (NGF0121 - PROTEGO-1). This fact implies that approximately 350 subjects will need to be screened in order to have 291 patients enrolled and at least 276 evaluable. In any case, the screen procedures should be interrupted when the expected sample size of 291 subjects has been reached.

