10.6.2 Primary Analysis of Efficacy Variables

The overall null hypothesis H_0 is that the change from baseline in the SANDE Global Score for at least one of the two concentrations of rhNGF ophthalmic solution (CCI and CCI) is greater or equal (worse and no improvement, respectively) than the vehicle one (μ_{VEHICLE}):

$$H_0: \text{CCI} \geq \mu_{\text{VEHICLE}} \text{ AND } \text{CCI} \geq \mu_{\text{VEHICLE}}$$

$$H_1: \text{CCI} < \mu_{\text{VEHICLE}} \text{ OR } \text{CCI} < \mu_{\text{VEHICLE}}$$

where for SANDE Global Scale lower score is better.

Considering the multiple comparisons (each concentration group versus vehicle) to claim superiority, a Bonferroni multiplicity correction of type I error will be applied on primary endpoint comparison. Each concentration group will be consequently tested at one-sided $\alpha = 0.0125$, in order to preserve the overall one-sided α of 0.025. The null hypothesis H_0 will be rejected if the associated primary analysis one-sided p-value will be lower than 0.0125 for at least one of the two concentration groups versus vehicle.

The primary endpoint (i.e., the change from baseline in SANDE global score at week 8) will be analyzed by means of a mixed model for repeated measures (MMRM) in the FAS. The analyses will include the fixed effects of treatment (3 levels: rhNGF C mcg/mL, rhNGF C mcg/mL and vehicle), visit (2 levels: Weeks 4, 8), baseline value, and treatment by visit interaction. The covariance matrix used will be "unstructured". Each concentration group (IMP1 and IMP2) will be compared with the vehicle group at Week 8 using the least square mean differences (i.e., the mean difference between each concentration group and vehicle over time). The model can be summarized as follows:

change from baseline

$$= \beta_0 + \beta_1 \text{treatment} + \beta_2 \text{base} + \beta_3 \text{visit} + \beta_4 \text{treatment} * \text{visit} + \varepsilon$$

where $\varepsilon \sim N(0, R)$ and R is the unstructured covariance matrix with blocks defined by the subjects. Further details and SAS code will be described in the SAP that will be generated before the DB lock and the unmasking.

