8.1.1. Primary Analysis

The overall null hypothesis H_0 is that the change from baseline in the SANDE Global Score for both of the two concentrations of rhNGF ophthalmic solution (μ_{DOSE5} and μ_{DOSE10}) are greater or equal (worse and no improvement, respectively) than the vehicle one ($\mu_{VEHICLE}$):

$$H_0 = \mu_{DOSE5} \geq \mu_{VEHICLE} \text{ and } \mu_{DOSE10} \geq \mu_{VEHICLE}$$

$$H_1 = \mu_{DOSE5} < \mu_{VEHICLE} \text{ or } \mu_{DOSE10} < \mu_{VEHICLE}$$

where μ denotes the mean change from baseline at week 8 in SANDE global score. For SANDE global Score, lower score is better.

Considering the multiple comparisons (rhNGF 5 mcg/mL versus vehicle, and rhNGF 10 mcg/mL versus vehicle) to claim overall superiority, a Bonferroni multiplicity correction of type I error will be applied on multiple comparisons. Each comparison will be consequently tested at one-sided alpha = 0.0125, in order to preserve the overall one-sided alpha of 0.025. The overall null hypothesis H_0 will be rejected if the associated primary analysis one-sided p-value will be lower than 0.0125 for one of two comparisons or both comparisons.

The primary analysis will be performed via Mixed-effects Model for Repeated Measures (MMRM) in the FAS according to the planned treatment. The analyses will include the change from baseline in SANDE global score as the dependent variable; the fixed effects of treatment (3 levels: rhNGF 5 mcg/mL, rhNGF 10 mcg/mL, and vehicle), visit (2 levels: Week 4, Week 8), baseline value, and treatment by visit interaction. An “unstructured” covariance matrix will be used. If the model fails to converge by using unstructured covariance matrix, compound symmetry matrix will be used instead. Each treatment group (IMP1 and IMP2) will be compared with the vehicle group at Week 8 using the difference in least square means (LS means) (i.e. difference between each concentration group and vehicle in mean change from baseline). The model can be summarized as follows:

$$\text{change from baseline} = \beta_0 + \beta_1 \text{treatment} + \beta_2 \text{base} + \beta_3 \text{visit} + \beta_4 \text{treatment} * \text{visit} + \varepsilon$$

where $\varepsilon \sim N(0, R)$ and R is the “unstructured” covariance matrix with blocks defined by the patients.

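### The primary MMRM applies one baseline slope to Weeks 4 and 8, so the Week 8 contrast is adjusted with a mix of the two visits' slopes; a baseline-by-visit term would remove this at almost no cost

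*SAP*

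**What the plan says.** All three descriptions of the primary model agree. Protocol 10.6.2 lists treatment, "visit (2 levels: Weeks 4, 8), baseline value, and treatment by visit interaction", and its equation has one coefficient for baseline. SAP 8.1.1 repeats this: "visit (2 levels: Week 4, Week 8), baseline value, and treatment by visit interaction". The code in SAP 13.3 is "model CHG=BASE TRTPN AVISITN TRTPN*AVISITN / DDFM=KR CL", with "repeated AVISITN/subject=USUBJID type=UN". No version contains a baseline-by-visit term.

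The SAP adds a fallback: "If the model fails to converge by using unstructured covariance matrix, compound symmetry matrix will be used instead". The primary comparison is the Week 8 difference in least-squares means, after multiple imputation has given every patient a value at baseline, Week 4 and Week 8.

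Elsewhere the SAP adjusts Week 8 outcomes with their own slope. SANDE severity and frequency are analysed by a separate ANCOVA at each visit (SAP 8.2.2.1), and modified strategy #2 uses a Week 8 ANCOVA (SAP 8.1.3).

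**The concern.** Treatment may differ by visit in this model, but the relation between baseline and change may not. Week 4 is the end of treatment. Week 8 follows four weeks on artificial tears, and Protocol 4.2 justifies the Week 8 endpoint by a symptom benefit that appeared after treatment stopped. The baseline slope could therefore differ between the visits, although nothing in the documents shows that it does.

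If the slopes differ, a chance baseline imbalance is corrected at Week 8 with a slope that is partly Week 4's. Some of the precision that baseline adjustment should bring to the primary comparison is then lost.

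**Working it through.** **The plan's own figure.** Inputs from Protocol 10.1: "observed mean changes (SD) were -28.2 (26.36) and -17.4 (20.29) for IMP and vehicle, respectively", and "the alpha level has been set to 0.0125 one-sided for each comparison".
- Difference: 28.2 - 17.4 = 10.8.
- Pooled SD: sqrt((26.36² + 20.29²)/2) = 23.52.
- Unequal-variance t-test at 92 per arm: power 80.2% (79.7% at 91).
- 92/0.95 = 96.8, so 97 enrolled per arm.

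The stated sample size reproduces. It sets the scale of the Week 8 SD. The documents give no Week 4 SD, Week 4/Week 8 correlation, baseline SD or slopes.

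**Assumptions used below.** Residual SDs s4 and s8 of 20 to 24; correlation r of 0.6 to 0.8; baseline SD of 12.5 (eligibility confines the score to 50-100); slope gap g between visits of 0 to 0.4; 97 per arm, 291 in total.

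**Share of the Week 4 slope.** With both visits present for every patient, generalised least squares gives a common slope of w4·b4 + w8·b8, where b4 and b8 are the visit slopes, w8 = 1 - w4 and

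w4 = (s8² - r·s4·s8) / (s4² + s8² - 2r·s4·s8).

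| s4, s8 | r | Calculation | w4 |
|---|---|---|---|
| equal, or compound symmetry | any | | 0.50 |
| 20, 24 | 0.6 | 288/400 | 0.72 |
| 20, 24 | 0.7 | 240/304 | 0.79 |
| 20, 24 | 0.8 | 192/208 | 0.92 |
| 24, 20 | 0.7 | 64/304 | 0.21 |

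**Effect on precision.** The between-arm baseline difference has variance 2 × 12.5²/97 = 3.22 (SD 1.79). Relative to the Week 8 contrast variance of 2·s8²/97:
- Borrowing the Week 4 slope adds (w4·g)² × 12.5²/s8².
- The common slope is estimated more precisely, which saves (1 - v/s8²)/288, where v = s4²·s8²·(1 - r²)/(s4² + s8² - 2r·s4·s8) and 288 = 291 - 3.

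For s4 = 20, s8 = 24, r = 0.7:
- v = 400 × 576 × 0.51/304 = 386.5, so the saving is (1 - 0.671)/288 = 0.11%.
- g = 0: net -0.11%, so the common slope is slightly better.
- g = 0.1: 0.17% - 0.11% = +0.06%.
- g = 0.2: 0.68% - 0.11% = +0.57%.
- g = 0.4: 2.71% - 0.11% = +2.6%.

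At g = 0.4 the net loss is 2.1% for r = 0.6 and 3.6% for r = 0.8. With s4 = 24, s8 = 20 and r = 0.7, the added variance at g = 0.4 is only (0.21 × 0.4)² × 156.25/400 = 0.3%. Three-arm simulations over gaps of 0 to 0.4 gave -0.1% to +2.5%.

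**Bias, error rate and power by simulation.** Three arms of 97, complete normal data, Week 8 SD 23.5, baseline SD 13 before truncation to 50-100, true difference 10.8:

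| Slopes at Weeks 4, 8 | s4, r | Power, common slope | Power, visit-specific slopes |
|---|---|---|---|
| -0.3, -0.3 | 20, 0.6 | 82.9% | 82.9% |
| -0.2, -0.5 | 20, 0.6 | 82.3% | 82.5% |
| -0.2, -0.5 | 18, 0.7 | 82.5% | 82.9% |
| 0, -0.5 (extreme) | 18, 0.7 | 80.2% | 82.3% |

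Mean estimates under the two models agree to about 0.01 point. Type I error is 0.0115-0.0116 with the common slope and 0.0116-0.0117 with visit-specific slopes, against a nominal 0.0125. In any one trial the two estimates typically differ by 0.1 to 0.5 points (one SD) in either direction.

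**The case against.** The strongest reply is that nothing here is an error. Protocol and SAP agree, a common-slope model is a legitimate prespecified choice, and randomisation protects it. That stands.

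A reader might infer that the Week 8 contrast is adjusted mainly with the Week 4 slope. The documents do not support this: it requires Week 4 to be the less variable visit, and no Week 4 variance is given. A reader might also infer that the wrong slope shifts the estimate. The shift has random sign and averages zero. Its mean absolute size was 0.13-0.46 points at gaps of 0.1-0.4 in a two-arm simulation, and 0.09 even with identical slopes, where it is estimation noise.

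It is also fair to say that the extra term is not entirely free. The common slope is marginally more efficient when the slopes are close, with break-even near a gap of 0.1. The protocol's amendment history records that the model equation was added at FDA's request, so changing it needs documentation. Both points stand, and both are small.

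**Conclusion.** This is a low-priority improvement to the primary model. That the Week 8 adjustment mixes two slopes follows from the model itself. How much of the mix is Week 4, and whether the slopes differ at all, rests on assumed values. The comparison is valid either way.

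The loss is negligible for gaps up to 0.1 and about 2.5% of variance at a gap of 0.4 with SDs of 20 and 24 and a correlation near 0.7. It is smaller if Week 4 is as variable as Week 8 or more so. Power changes by less than 0.5 points in ordinary scenarios and by about 2 points in the extreme one, and the required sample size does not change materially. The simulations assume complete, normal, homogeneous data and do not model the imputation.

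The term is still worth adding. The possible gain exceeds the possible loss, no new data are needed, and the primary analysis would then use the same kind of Week 8 baseline adjustment as the SANDE component scores and modified strategy #2.

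**What to change.** In SAP 8.1.1 and 13.3, specify `model CHG=BASE TRTPN AVISITN BASE*AVISITN TRTPN*AVISITN / DDFM=KR CL`. Carry the term into every analysis that reuses this model: the missing-at-random, tipping-point, complete-case, observed-case and per-protocol analyses, modified strategy #1, and the Week 4 SANDE Global Score comparison. Keep it under the compound-symmetry fallback too.

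Record the change in SAP section 11 as a departure from the equation in Protocol 10.6.2. Make it before unmasking: a later addition would be a post-hoc change to the primary model, and the note beneath the code allows adjustments only for modified estimands and sensitivity analyses.

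The cost is one extra fixed-effect parameter, about 0.1% of precision if the slopes are truly equal, and the documentation of the departure.
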